12.0 Provisions to Monitor the Data to Ensure the Safety of Subjects*

PROTOCOL TITLE: The Effects of Core Activation and Stabilization Training on Gait Kinetics, Kinematics, and Speed, and Self-Perceived Function in Patients with Knee Osteoarthritis

12.1 NA; pending the IRB agreeing with the PI that there is no more than minimal risk to participants in this investigation.

13.0 Withdrawal of Subjects*

13.1 Participants in the experimental group will be withdrawn from participation without their consent if they miss more than four of the total 12 sessions throughout the entire intervention program. They will also be removed if they do not perform the home exercise program at least once a week.

13.2 Immediately upon meeting the criteria for termination from participation, the participant will be informed in-person or by phone by the PI.

13.3 If participants withdraw from the research, including partial withdrawal with some data collection having already been completed, data already collected will be used in data analysis, unless the participant specifically requests otherwise. Additionally, they will not participate in any further aspects of the investigation, after following the procedures from 13.1 and 13.2. The same will be done for participants who withdraw of their own volition.

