than three participants will undergo the training simultaneously. Training sessions will not be performed on consecutive days in an effort to reduce the chances of delayed onset muscle soreness being present during treatment sessions. Additionally, the core training program includes predetermined guidelines on exercise progressions in order to ensure that the exercises are not progressed too rapidly. The PI will be present and will lead all sessions, ensuring that the exercises and their progressions are done correctly.

After the completion of the intervention program, each participant will undergo gait analysis in the same manner mentioned in Part 1, with the exception of no anthropometric data being collected.

Participants will then complete a second, post-intervention KOOS questionnaire, and turn in their home exercise program sheet with tallies from completed sessions. Please see Part 1 for completion of the pre-intervention KOOS questionnaire.

9.3 The table below details the procedures and occurrence of those procedures throughout a single participant's participation in the investigation:

Procedures	Occurrence
Education/Informed Consent	1 all participants
Anthropometric Data Collection	1 all participants
Baseline (Part 1) Without & With Core Activation (Part 2) Pre 6-Week Intervention Gait & EMG Assessment (Part 3)	1 all participants (except no part 3 for controls)
Pain NPRS Assessment	2 for KOA group
Core Stability Intervention Program	12 sessions, plus 18 home program sessions (KOA group only)
Post 6-Week Intervention Gait & EMG Assessment	1 (KOA group only)
Pre and Post 6-Week Intervention KOOS Assessment	2 (KOA group only)

9.4 The exclusion criteria serve to prevent participation of those who require assistance or assistive devices for ambulation, so safety during the ambulation activities is minimized. The adhesive tape used in reflective marker placement is intended for placement on the skin. Regarding PHI, the PI will be the only investigator involved in the recruitment and consent process and will be charged with

PROTOCOL TITLE: The Effects of Core Activation and Stabilization Training on Gait Kinetics, Kinematics, and Speed, and Self-Perceived Function in Patients with Knee Osteoarthritis

protecting the PHI in his office. The motion analysis data and PHI will be protected in the manner discussed in sections 11.3.

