A tape measure, body weight scale, EMG biofeedback with electrodes, and Vicon Vero 2.2 Motion Analysis System, and reflective markers with tape will be used. Exercise equipment will include exercise mats/high-low exercise tables, ankle weights, hand weights, BOSU balls, and resistance bands.

Please see the attached Excel file that will be used for data collection, in addition to the script for instructions to patients and KOOS questionnaire.

- 9.5 There is no long-term follow-up for this study apart from the final data collection session for the experimental group after completing the six-week intervention. This session will include another motion analysis session and post-treatment KOOS questionnaire completion.
- 9.6 NA.

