10.0 Data and Specimen Banking*

- 10.1 A repository will be used to store all of the gait kinetic, kinematic, and speed data collected during the motion analysis sessions. This data will be stored on the computer system in the Gait Lab which is password protected, in addition to the lab itself being key access. The Data Collection Form (see attached), in addition to completed Core Program Tracker for Investigator Use and KOOS forms (see attached) will be included in the repository. This data will be kept in the PI's office which is key access, with the Data Collection Form staying on the PI's password protected personal laptop or state desktop computer, with the hardcopy KOOS and Core Program Tracker for Investigator Use forms will remain in the hardcopy compliance binders. The data will be stored for a period of seven years. Persons using the Gait Lab will have access to this data but will require IRB approval for use in research activities.
- 10.2 The repository data will include all force plate data and that collected from the infrared cameras, including pelvis, hip, knee, and ankle joint moments, range of motion in all three planes, and spatiotemporal gait characteristics, in addition to anthropometric data, KOOS scores, pain NPRS ratings, and exercise data from the Core Program Tracker for Investigator Use form.
- 10.3 In order for the data to be accessed for research purposes, a new approved IRB protocol will be required. Additionally, if the author

PROTOCOL TITLE: The Effects of Core Activation and Stabilization Training on Gait Kinetics, Kinematics, and Speed, and Self-Perceived Function in Patients with Knee Osteoarthritis

of said protocol is not the PI or the sub-investigator, they will need to request permission from one of these investigators prior to including this request in their proposed research protocol.

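### KOA participants withdrawn for low adherence get no post-test, so the Aim 3 pre-post change and the H3 regression rest on people selected on adherence after baseline

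*Combined protocol and SAP*

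**What the plan says.** Section 13.1 gives two grounds for withdrawing a KOA participant without consent. The first applies "if they miss more than four of the total 12 sessions throughout the entire intervention program". The second concerns home exercise: "They will also be removed if they do not perform the home exercise program at least once a week".

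Section 13.3 sets the consequence. Of data in hand it says "data already collected will be used in data analysis, unless the participant specifically requests otherwise"; of the participant it says "they will not participate in any further aspects of the investigation". That sentence refers back to 13.1 and 13.2, so it covers withdrawal imposed by the investigator as well as voluntary withdrawal.

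The post-test comes only at the end. Section 9.2 (Part 3) has "After the completion of the intervention program, each participant will undergo gait analysis", followed by the second KOOS and the hand-in of the home exercise sheet. The 9.3 table lists one "Post 6-Week Intervention Gait & EMG Assessment", for the KOA group only. Section 9.5 rules out any later follow-up apart from "the final data collection session for the experimental group after completing the six-week intervention".

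Aim 3 (1.1, 1.2) is worded for participants with KOA, without restriction to completers. Its H3 asks whether total supervised plus home sessions predicts change. Section 11.1 plans means comparisons, ANOVA or MANOVA, and a regression on session number. It names no analysis set and no method for a missing post-test.

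**The concern.** A person withdrawn in, say, week four has a baseline gait analysis and KOOS but no planned second measurement. The baseline data that 13.3 keeps cannot form a change score, so every Aim 3 comparison becomes a comparison among people who met an adherence standard after enrolment. The plan does not name that group as its target.

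Two things are at stake. If people who do more sessions improve more, the observed mean change is larger than it would be in the enrolled KOA group. And H3 asks about dose while the rule withholds the outcome from many of the people with low doses, who carry most information on that question. A null H3 result would then be hard to read. A post-test that was never taken cannot be recovered at the analysis stage.

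**Working it through.** **Session arithmetic.** From 9.2: 2 per week × 6 = 12 supervised and 3 per week × 6 = 18 home, total 30. This agrees with the 9.3 table.

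**Lowest total a retained person can have.** Supervised rule alone: 12 − 4 = 8 supervised + 0 home = 8 of 30. With the home rule also enforced during the program: 8 + 6 × 1 = 14 of 30.

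**Highest totals that are still removed.** The rules act on the components. A person with 7 supervised + 18 home = 25 sessions is withdrawn. So is a person with 12 supervised + 15 home = 27 and one empty home week, if the lapse is noticed in time. In the simulation below (mean adherence 0.90), 92-100% of those removed by the supervised rule have totals of 8 or more, and 72-100% of those removed by both rules have 14 or more.

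**Attrition in the plan.** Section 11.2: 45 / (1 − 0.10) = 50, which reproduces. It allows 5 losses. Controls attend once (7.1), so intervention losses fall on the KOA group: 25 − 5 = 20 left if all five are KOA, or 25 × 0.90 = 22.5 if the 10% applies to that group alone. How much of the 10% is 13.1 withdrawal is not stated.

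**Retention if everyone has the same completion probability p (assumed), sessions independent.** Supervised rule: P(Bin(12, p) ≥ 8). Home rule: [1 − (1 − p)³]⁶.

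| p | Supervised rule | Home rule | Both |
|---|---|---|---|
| 0.9 | 0.996 | 0.994 | 0.990 |
| 0.8 | 0.927 | 0.953 | 0.884 |
| 0.7 | 0.724 | 0.849 | 0.614 |

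**Simulation with varying adherence.** Assumed: p ~ Beta(mean·k, (1 − mean)·k), where smaller k means more variation between people; supervised ~ Bin(12, p); home = six weeks of Bin(3, p); change = r·z(total sessions) + √(1 − r²)·noise; 25 KOA participants; two-sided test at 0.05. Withdrawn people are given the count they would have reached without the rule. Mean 0.90, r = 0.5:

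| Adherence | H3 power, all 25 tested | H3 power, supervised rule | Mean shift (SD), supervised rule | H3 power, both rules | Mean shift (SD), both rules |
|---|---|---|---|---|---|
| Same for all | 75% | 74% | about 0.01 | 73% | 0.01 |
| Mild variation (k = 30) | 74% | 69% | 0.02 | 67% | 0.03 |
| Strong (k = 10 to 3) | 73-70% | 59-35% | 0.05-0.11 | 54-29% | 0.07-0.13 |

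Retention runs from 99.6% to about 92% under the supervised rule and from 99% to 90% under both. A small loss of people can cost much power because the predictor loses spread: under both rules its SD falls to 0.80, 0.66 and 0.55 of the full value at k = 10, 5 and 3.

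**Sensitivity.** The mean shift is r × (mean z among those retained). It is zero at r = 0, and at r = 0.2 the supervised-rule maximum is 0.11 × 0.2 / 0.5 ≈ 0.04 SD. H3 power at r = 0.2 under both rules is 15% down to 8%, against 16%. At mean adherence 0.80, r = 0.5, both rules: 88-76% retained, power 61-21%, shift 0.08-0.23 SD.

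**Slope.** In this model the slope stays at about 0.50, because change depends linearly on the total alone. If instead only supervised sessions drive change (r = 0.5, supervised rule), the slope on the total moves from 0.32 to 0.31 with uniform adherence and from 0.47 to 0.40 at k = 3.

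**The case against.** Section 13.1 openly defines adequate participation, and a completer question is a legitimate reading of Aim 3. On that reading nothing is overstated and only a label is missing. That stands, and the fix allows for it.

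The size is assumed throughout. Section 2.1 reports high compliance with core training in older adults, and 11.2 allows only 10% attrition. With uniformly high adherence almost nobody is withdrawn. H3 is not among the comparisons listed in the 11.2 power analysis, so its loss is not measured against a planned figure. All of this stands.

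The home rule may have little effect in practice. Home sheets are handed in at the post-intervention visit and no earlier check is described, so a lapse may surface only after testing, when 13.3 keeps the data. The supervised-rule figures are therefore the better supported ones.

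Testing withdrawn people does not undo the rule. Their exercise is still stopped, so their low counts are partly produced by 13.1, and a mean that includes them answers a different question. If sessions end in the week of withdrawal (mean 0.90, r = 0.5, both rules), all-tested H3 power is 78-84% and the two means differ by 0.03-0.20 SD. This stands too; the analysis has to say which question it answers.

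A reader might infer that H3's predictor is simply cut off at 8 or 14 sessions. It is not: those are floors, and people with high totals are removed as well. A reader might also infer either that the H3 slope is invalid or that it is certainly unaffected. The documents support neither. It is unbiased only if change is linear in the total, supervised and home sessions act equally, and adherence is otherwise unrelated to change. The protocol gives no ground for assuming equal effects, since supervised sessions are led by the investigator and home sessions are done alone.

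**Conclusion.** The gap holds on the text: a KOA participant withdrawn during the program has no planned post-test, no method in 11.1 makes up for it, and Aim 3 is not stated as a completer aim. Its Aim 3 results will describe people selected on adherence after baseline.

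The consequence is conditional. Mean change is overstated only if more sessions go with more improvement. A reader might conclude that the pre-post result must be inflated; the documents do not show that. H3 loses precision, by an amount that depends on how much adherence varies between people. At assumed mean adherence 0.90 and r = 0.5, the supervised rule ranges from negligible (99.6% retained, power 74% against 75%) to material (about 92% retained, power 35% against 70%, mean shift about 0.11 SD). The textual gap is certain; its size is not. It should be corrected before recruitment because the correction is cheap and the missing data cannot be recovered later.

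**What to change.** In 13.3, separate stopping the exercise sessions from stopping assessment. Offer the post-intervention gait analysis and KOOS already listed in 9.3, at the originally scheduled post-program time, to every KOA participant who has not withdrawn consent. Keep their session counts from the "Core Program Tracker for Investigator Use" form (10.1) and the home sheet.

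In 11.1, use everyone with a post-test in the Aim 3 and H3 analyses. State that this mean includes people whose program was stopped under 13.1, and report the threshold-meeting group as a sensitivity analysis. If a completer question is intended, say so and label the result accordingly. The withdrawal thresholds are left to the sponsor.

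Cost: protocol wording and a few extra visits. At mean adherence 0.90 under the supervised rule, that is 25 × (1 − 0.996) = 0.1 to 25 × (1 − 0.92) = 2 people; at 0.80 under both rules, 25 × 0.12 = 3 to 25 × 0.24 = 6. Some withdrawn people may not return. If half do (0.90, r = 0.5, both rules), H3 power is 74% with uniform adherence, 71% with mild variation and 64-53% with strong variation, and the mean shift is about halved. The average change may look smaller.

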14.0 Risks to Subjects*

14.1 The only foreseeable risk/discomfort a participant may have is some muscle soreness within 48 hours from the ambulation and TA muscle contractions involved in Part 2, or the same after participation in the core stability exercises included in Part 3. This soreness is considered a normal effect of muscular exercise. Also, there is a possibility of the adhesive tape, used during marker placement in the motion analysis data collection, pulling any hair present on the skin when removed.

14.2 NA.

14.3 NA.

14.4 NA.

15.0 Potential Benefits to Subjects*

15.1 There is a possibility of direct benefits to half of the participants (group with KOA) in Part 3 of the investigation, but no guarantee. This investigation focuses on a novel intervention to improve the gait and function of patients with KOA. Therefore, the purpose of

PROTOCOL TITLE: The Effects of Core Activation and Stabilization Training on Gait Kinetics, Kinematics, and Speed, and Self-Perceived Function in Patients with Knee Osteoarthritis

this investigation is whether or not this intervention will have direct beneficial effects.

15.2 There is no possibility of a direct benefit, besides knowledge of current gait and functional ability for Parts 1 and 2 of this investigation; however, there is a possibility of direct benefit after participation in the core stability intervention program included in Part 3 if the program is found to improve gait and function in participants with KOA.

16.0 Vulnerable Populations*

16.1 NA.

17.0 Community-Based Participatory Research*

17.1 NA.

18.0 Sharing of Results with Subjects*

18.1 No individual participant results will be provided. Participants will be provided with the PI's contact information if they wish to know the results of the investigation after their participation is completed, and data analysis is completed.

19.0 Setting

19.1 All recruitment, informed consent, data collection, and data analysis will be completed in the SAHP at LSU Health-Shreveport. Data collection will be performed in the Gait Lab in the SAHP. The intervention program will take place in the RFP Clinic in the SAHP.

20.0 Resources Available

20.1 The PI is a licensed physical therapist, with board-certification in orthopaedic physical therapy, and is a PhD candidate at Texas Woman's University in the School of Physical Therapy. The PI has training in motion analysis. The sub-investigator has a PhD in Biomedical Engineering and is licensed as a Professional Engineer in Electrical Engineering. He also runs the Gait Lab in the SAHP. Both investigators are full-time faculty in the SAHP, the first as Assistant Professor and the later as Professor with tenure.

20.2 Participants will be recruited from within the University and from outside sources in the greater Shreveport area. With KOA being so prevalent, the PI does not foresee any difficulty in recruiting the necessary sample size. Additionally, the recruitment methods

PROTOCOL TITLE: The Effects of Core Activation and Stabilization Training on Gait Kinetics, Kinematics, and Speed, and Self-Perceived Function in Patients with Knee Osteoarthritis

include assistance from other clinicians and departments, in addition to public advertising, enabling the PI to broaden the opportunities for recruitment (see 22.0).

The PI has an FTE percentage of 30% dedicated to research in the LSU-Health Shreveport system, therefore up to 12 hours a week will be available for completing this project. This will be the only research project the PI is lead investigator on during the duration of this investigation. Additionally, the sub-investigator's research FTE percentage is 40%, so he has up to 16 hours per week to devote to this project, among others.

The Gait Lab is located on the second floor (room 2-217) in the SAHP. The lab is 700 square feet, and has a Vicon Vero 2.2 (12 camera) motion analysis system with 2 AMTI force plates embedded in the raised platform (8 x 24 ft). The Gait Lab has an EMG system which is integrated with the motion analysis system, and will be used to collect the EMG data during the walking trials. There are two desktop monitors connected to the computers used for data collection and analysis for viewing of output and processing. The RFP Clinic is located on the ground floor of the SAHP and is a 27,000 square foot facility with a large open gym area and private treatment rooms.

The PI has designed the investigation, completed all of the IRB submission requirements, and pursued avenues for recruitment of participants; therefore, he is familiar with the protocol. The sub-investigator has been informed and consulted throughout the process, and therefore has a good understanding of the purpose and specific aims of the study. He will be provided a copy of the protocol to review prior to commencement of the investigation.

21.0 Prior Approvals

21.1 Prior to commencing the research, approval of the study via an Institutional Authorization Agreement (IAA) with Texas Woman's University in Houston (TWU) will be required since this investigation is being used in partial fulfillment of the PI's PhD degree as the dissertation research. No data collection or recruitment will be done at this site.

22.0 Recruitment Methods

PROTOCOL TITLE: The Effects of Core Activation and Stabilization Training on Gait Kinetics, Kinematics, and Speed, and Self-Perceived Function in Patients with Knee Osteoarthritis

22.1 Participant recruitment will start immediately after IRB approval is obtained, and the IAA is signed by TWU. All recruitment will be managed through LSU Health-Shreveport and will be focused in the Shreveport area. No recruitment will be done through TWU.

Potential participants will be recruitment in multiple ways, including word of mouth, e-mailed flyers through the LSU Health-Shreveport Public Relations Department's Friday flyer, e-flyer postings on the announcement TVs in the SAHP, e-flyers posted on social media (including Facebook), flyer placements in the RFP Clinic in the SAHP, hard-copy and EHR (TherapySource, Advanced MD, and EPIC) chart reviews in through the RFP Clinic in the SAHP, flyer postings throughout the community (ex. gyms, churches, etc.), and through coordination with departments in the Medical School and area physical therapy clinicians/clinics. The PI will request assistance from the Departments of Family Medicine, Rheumatology, and Orthopaedic Surgery, among any others identified, to identify potential participants, in addition to posting flyers. This will also include the Rehabilitation Sciences Department in Ochsner-LSU Hospital. This cooperation with other departments may also include chart reviews for each respective clinic in the EPIC system to screen for potential participants who may qualify for the study prior to approaching them while in their clinic visits. The PI will also contact area therapists and therapy clinics asking them to do the same. If the PI does not recruit the participant in person, they will be contacted via telephone using the script attached to this protocol (see Telephone Script.v1.docx).

22.2 Participants will be primarily those living in the Shreveport area, and may also include previous/current patients in the RFP Clinic.

22.3 Once a potential participant expresses interest and contacts the PI, or once the PI contacts them, the PI will ensure they meet the inclusion/exclusion criteria.

22.4 Both printed and e-versions of the same flyer will be used to recruit participants. Please see attached.

22.5 NA.

23.0 Local Number of Subjects

23.1 Fifty participants (N = 50), 25 healthy controls and 25 with a diagnosis of KOA will be recruited for the purposes of this investigation.

23.2 Refer to the *a priori* power analysis provided in section 11.2.

PROTOCOL TITLE: The Effects of Core Activation and Stabilization Training on Gait Kinetics, Kinematics, and Speed, and Self-Perceived Function in Patients with Knee Osteoarthritis

